We will examine subjects at the level of functional disability (i.e. clinical rating scales), at the level of impairment (i.e., strength and sensation), and at the level of anatomy (i.e., MTI and DTI). The general paradigm includes four parts, requiring 1.5-3.5 hours for testing, depending on the number of activities done. Part 1 is the clinical neurological evaluation which includes clinical rating scales along with measures of lower extremity impairments and quality of life, requiring one hour. Part 2 is the laboratory testing of global walking requiring 30 minutes. Part 3 is evaluation and instruction for a custom exercise program, requiring one hour. Part 4 involves conventional imaging and measures of DTI and MTI in the brain and spinal cord to be completed in the F.M. Kirby Center in KKI, across the hall from the Motion Analysis

Date: July 1, 2013
Principal Investigator: [name]
Application Number: NA_00045673

Laboratory (requiring one hour). We will allow rest breaks as needed by each individual. Parts 1, 2, and 3 will be conducted at the Motion Analysis Laboratory located in KKI. All subjects will participate in 3 testing visits, one at baseline, one at 12 weeks and one at 18 weeks from the baseline visit. All subjects will be asked to participate in parts 1-4 at the baseline visit, and only parts 1 and 2 during visits 2 and 3.

Thus, for testing the breakdown for the time is as follows:

Baseline visit: 1 hr. clinical exam, 30 min. gait test, 1 hr. exercise instruction, 1 hr. MRI scan

12th week visit: 1 hr. clinical exam, 30 min. gait test

18th week visit: 1 hr. clinical exam, 30 min. gait test

All subjects will undergo a functional sensorimotor assessment at every testing session with the purpose of systematically documenting clinical status. The primary investigator or physical therapist and research coordinator will conduct this exam. The exam will include standard clinical measures of sensation (vibration, proprioception), strength, tone (Modified Ashworth), and passive range of motion. In addition, we will use standardized quantitative scales to evaluate walking, ataxia, and overall disease impairment in these individuals. Lastly, self report measures of quality of life and pain will be used.

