After the functional assessment, locomotion will be evaluated. Each subject will be asked to walk several times across a 25-foot walkway to evaluate locomotion, and to stand still on a force plate to evaluate balance; all movements will be done in the Motion Analysis Laboratory at the Kennedy Krieger Institute. To track walking we will use a GaitRite System. This is a walkway that has pressure activated sensors that measure the temporal (timing) and spatial (two dimension geometric position) parameters of the foot as it lands on its pressure activated sensors. For balance, a vital component of locomotion, we will assess the extent of postural sway while standing on a static force plate. The force plate is embedded in the floor of the laboratory and is very sensitive to small amounts of movement that are often missed by observation. Force plate data will be collected at 1000HZ using a Kistler 9281 force plate (Kistler Instrument Corp., Switzerland). During these tasks we may also evaluate muscle activity using electrodes to record surface electromyography (EMG) signals. Markers will be pasted on the surface of the skin over relevant muscle groups. Data from the EMG markers will be collected at 1000Hz and time locked using Optototrak software. During all movements an examiner will guard each subject and rest breaks will be given as needed.

To begin the exercise intervention a physical or occupational therapist will evaluate their strength, flexibility, and level of activity. Then subjects will be given an exercise program to follow at a designated fitness facility. The physical or occupational therapist will teach the subject how to do each exercise and tell them where they will be done. The progressive resistance training program will consist of 12 weeks of guided resistance training 3 times weekly. Subjects will be asked to do one day of resistance training at their home weekly. A member of the research team (i.e., a physical or occupational therapist or research coordinator) will contact each subject by phone or email several times over the first 12 weeks of the study to answer any questions and encourage subjects to continue with their exercise program. Compliance will be tracked by the facility (i.e., Curves). They will send the PI monthly reports stating the number of times each participant has used the facility. Subjects will also be given an

Date: July 1, 2013
Principal Investigator: [name]
Application Number: NA_00045673

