c. Blinding, including justification for blinding or not blinding the trial, if applicable.

All subjects in the study will take part in the exercise intervention. We are unable to blind the subjects or testers to the intervention which has been discussed in other similar studies as a limitation. However, we have specified guidelines that the PT will follow for progression of the exercise program to alleviate bias as much as possible.

d. Justification of why participants will not receive routine care or will have current therapy stopped.

N/A

Date: July 1, 2013
Principal Investigator: [name]
Application Number: NA_00045673

e. Justification for inclusion of a placebo or non-treatment group.

N/A

f. Definition of treatment failure or participant removal criteria.

Patients selected for the study will be removed if they: 1) inform us that they become pregnant during the study, 2) are unable to follow the requirements of the study, or 3) request to be removed.

We are not aware of a particular pregnancy risk, but the inclusion of a subset who are pregnant would be difficult to interpret compared to non-pregnant participants.

g. Description of what happens to participants receiving therapy when study ends or if a participant's participation in the study ends prematurely.

The subject's medical care will continue unaltered when the study ends or if a subject is removed from the study.

5. Inclusion/Exclusion Criteria

Inclusion criteria for women with X-ALD

- confirmed diagnosis, X-ALD heterozygote carrier
- no medical contraindication to participating in a strength training program
- able to follow complex directions as determined by a score of ≤ 1 on a subset of questions taken from the NIH Stroke scale (Brott et al. 1989)
- hip flexion strength: 6.6-15.8kg or hip extension strength: ≤ 18.3 kg
- normal passive range of motion at hips/knees/ankles
- scale of 1-6 on the EDSS
- able to walk ≥ 50 m
- age 21-65

Exclusion criteria

- Evidence of other neurological deficit that could interfere, such as previous stroke or muscle disease
- congestive heart failure
- cancer
- orthopedic conditions
- severe pain that precludes study participation
- seizures
- pregnancy
- other medical condition that precludes participation in an exercise program, e.g., unstable angina, uncontrolled diabetes, uncontrolled hypertension

Date: July 1, 2013
Principal Investigator: [name]
Application Number: NA_00045673

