The potential risks in this study are very low. The study is entirely non-invasive. Subjects may become fatigued or lose their balance during walking or standing and they may have slight muscle soreness, this has occurred very rarely in past studies. There is a potential that subjects may have an allergy/sensitivity to the tape used for marker placement, in this situation we will use a stocking net that we have in the lab to hold the marker in place instead of tape. Subjects may become uncomfortable while in the MRI scanner. Any incidental findings on MRI will be provided to the patient by [name] by phone or if necessary in a clinical visit. If there are new findings the individual will be assisted in obtaining follow up care. There is a potential risk of time commitment (missing work or school) and therefore we will be flexible and practical in scheduling convenient appointments.

- b. Steps taken to minimize the risks.

Date: July 1, 2013
Principal Investigator: [name]
Application Number: NA_00045673

All subjects will complete the exercise intervention with supervision. A licensed physical or Occupational therapist will progress the exercise intervention for each individual based on their capabilities. Subjects will be given rests whenever needed or requested.

During the walking and balance tests we will place a gait belt on all subjects and 1-2 investigators will walk behind them in case they lose their balance. We will also give a rest break when subjects feel fatigued, short of breath, or simply want a break. They will be allowed to stop any test at any time or rest between tests. In previous studies there has been no incident that would suggest any significant potential risk.

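### The only bias safeguard in section 4c governs how training is progressed, not how outcomes are tested, and a woman's own trainer or caller may score her effort-dependent outcomes

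*Combined protocol and SAP*

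**What the plan says.** Section 4c (Blinding) states: "We are unable to blind the subjects or testers to the intervention which has been discussed in other similar studies as a limitation". The sentence that follows is the only mitigation given: "However, we have specified guidelines that the PT will follow for progression of the exercise program to alleviate bias as much as possible".

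The staffing is described elsewhere:

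- **Examination at every testing session** (section 4a, functional sensorimotor assessment): "The primary investigator or physical therapist and research coordinator will conduct this exam".
- **Teaching the exercises** (section 4a, exercise intervention): "The physical or occupational therapist will teach the subject how to do each exercise".
- **Progressing the training** (section 7b): "A licensed physical or Occupational therapist will progress the exercise intervention for each individual based on their capabilities".
- **Contacts during the first 12 weeks** (section 4a, exercise intervention): "A member of the research team (i.e., a physical or occupational therapist or research coordinator) will contact each subject by phone or email", with the purpose "to answer any questions and encourage subjects to continue with their exercise program".

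Study Statistics (a) makes FS the primary outcome for the exercise intervention. It is built from sit to stand, Up and Go, the 25-foot timed walk and the 6-minute walk. Hip and ankle strength is among the primary impairment outcomes. Study Statistics (b) lists, for response to exercise, an unpaired t test of pre-to-post differences between groups and paired t tests within groups. Section 4c also says that every subject exercises, so there is no untrained arm.

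**The concern.** Guidelines for progression control what is delivered between visits. They have no bearing on how a maximal strength effort or a timed walk is instructed, encouraged or recorded at a visit. Section 4c nevertheless presents them as its answer to bias straight after conceding that testers are unblinded.

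Strength and the four FS tests depend on the subject's effort, and effort responds to the tester. A tester who has taught a woman her programme, or has telephoned to encourage her, has an interest in her progress and a rapport that was absent at baseline. The Abstract also records that the team expects many of the women to improve. Extra encouragement at week 12 or week 18 would then appear as gain. With no untrained arm, the within-group tests cannot subtract it.

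**Working it through.** **1. Role overlap.** The plan names roles, not individuals.

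| Role | Examines (4a) | Teaches (4a) | Progresses (7b) | Contacts (4a) |
|---|---|---|---|---|
| Investigator | yes | not named | not named | not named |
| Physical therapist | yes | yes | yes | yes |
| Occupational therapist | not named | yes | yes | yes |
| Research coordinator | yes | not named | not named | yes |

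Two of the three examining roles may also train or contact the same woman. No section requires a different person, and none fixes the wording or encouragement used during testing. The plan does not say specifically who administers the four FS tests. Overlap is therefore possible but not certain.

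**2. Which analyses are exposed.** Let b be a constant shift in the post-training score.

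- Within-group paired test: the mean change becomes (true change + b). It is fully exposed.
- Carrier-versus-control unpaired test of change: (carrier change + b) − (control change + b) = carrier change − control change. A common b cancels; only a difference in b between groups remains.
- Objective 2 correlations and regressions of response on MTR and FA: adding a constant to every woman's response alters the intercept only. Slopes and correlations are unchanged. If overlap applies to some women and not others, b varies between women and can add noise. The documents give nothing from which to size that.
- Objective 1 at baseline: imaging is done at baseline, before any training or encouragement contact, so this mechanism does not reach the baseline associations.

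**3. Size.** The plan gives no figure for tester-related shift, so there is none to reproduce. The calculation is hypothetical. Inputs from Study Statistics (c): two-sided alpha 0.05, n=12 (minimum carriers) and n=15 (planned carriers). Assumptions: zero true change, and the same shift δ, in SDs of change, in every woman.

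Rejection probability = P(|T| > t(0.975, n−1)), where T is noncentral t with n−1 degrees of freedom and noncentrality δ√n. The critical values are 2.201 (n=12) and 2.145 (n=15). For example, with δ=0.2 and n=12 the noncentrality is 0.2 × √12 = 0.693.

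| Assumed δ | n=12 | n=15 |
|---|---|---|
| 0.1 | 6.2% | 6.5% |
| 0.2 | 9.7% | 11.2% |
| 0.3 | 15.8% | 19.2% |
| 0.4 | 24.5% | 30.3% |

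**4. The same range on the strength scale.** Study Statistics (c) gives hip flexion as 11.2 ± 4.6 kg. With an assumed pre-post correlation r, which the documents do not give, the SD of change is 4.6 × √(2(1−r)): 3.56 kg at r=0.7 and 2.06 kg at r=0.9. A 5% shift is 0.05 × 11.2 = 0.56 kg, so δ is 0.56/3.56 = 0.16 to 0.56/2.06 = 0.27. The paired test then rejects in 7.9% to 13.9% of trials at n=12 and 8.8% to 16.6% at n=15. If that shift arose in one group only, the unpaired test would reject in 6.6% to 9.8% at 12 per group.

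**The case against.** The strongest reply is that little of the plan is exposed. The first-listed group comparison is the unpaired test, where a common shift cancels because controls train and are tested on the same schedule. Objective 2 concerns who responds, and a constant shift does not touch its correlations or slopes. Both points stand, and they confine the concern mainly to the within-group tests. Without an untrained arm those tests already cannot separate training from practice, so tester overlap adds to a larger limitation.

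The plan also has partial protections. Section 4a describes a standardised examination and standardised scales, and it uses an instrumented walkway and a force plate. Section 4c discloses the lack of blinding openly. These help consistency and recording, but they neither separate tester from trainer nor control encouragement.

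Three stronger readings are tempting, and the documents do not support them:

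- *That trainers will test their own women.* The investigator is a named examiner with no training or contact duty, and an occupational therapist may do the training without being a named examiner. The text permits overlap; it does not prescribe it.
- *That the false-positive rate is materially inflated.* The shift is assumed. At 0.1 SD the rate is 6.2% to 6.5%, close to nominal, and the calculation applies the shift to every woman.
- *That the progression guidelines serve no purpose.* Section 4c does not say which bias they address. They can reasonably limit uneven delivery of training.

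**Conclusion.** The concern holds in a limited form. The mitigation in 4c does not address measurement bias, and the plan lets a woman's trainer or caller obtain her strength and FS scores. The planned within-group paired tests are the analyses mainly at risk. An upward direction is a reasonable inference from the stated expectation of improvement; the documents do not demonstrate it. The rejection rates above illustrate sensitivity under an assumed shift and do not estimate what this trial will show. The carrier-control contrast is affected only if the shift differs between groups, and objective 2 only if overlap is uneven between women. This is a worthwhile, inexpensive improvement and does not invalidate the design.

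**What to change.** Amend section 4c and the examination paragraph of section 4a as follows.

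1. At baseline, week 12 and week 18, strength and the four FS tests are administered by staff already named for the examination who do not teach, progress or make encouragement contacts to that woman. One workable split is the investigator with the coordinator for testing, leaving instruction, progression and contacts to the therapists. Record any unavoidable exception.
2. Use one fixed script for test instructions and encouragement, at all visits and in both groups.
3. Reword 4c to say that the progression guidelines limit uneven delivery of training and do not address measurement bias. State that measurement bias remains a limitation, because even a separate tester knows that everyone trained.

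The cost is protocol wording, a short script and planning of who tests whom. The downside is less scheduling flexibility. The documents do not give staff numbers, which is why exceptions should be allowed and recorded. Sample size, visits, outcomes and the exercise programme are unchanged.

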Conventional magnetic resonance imaging techniques along with the Loes scale (i.e., categorical rating scale) have been used to evaluate progression of X-ALD disease burden in children with moderate success. Pathologic studies show that dying back of axonal loss is a primary pathogenic mechanism of AMN and much of the permanent disability results from axonal damage. However, attempts at correlating clinical disability with axonal injury have had limited success due to clinical rating scales that do not adequately measure all aspects of the disease, coupled with an inability for routine imaging techniques to depict specific clinically involved fiber tracts in the brain and spinal cord. Our preliminary data show that we can distinguish female carriers from control subjects using novel techniques such as magnetization transfer (MT) imaging. In addition, we have previously shown that damage measured using tract specific MRI, specifically magnetization transfer and diffusion tensor imaging (DTI) correlates with physical impairments in individuals with the degenerative disease of multiple sclerosis.

In conjunction with advanced DTI and MT metrics developed at the Kirby Imaging Center of the Kennedy Krieger Institute, we plan to capitalize on the tools within our motion laboratory, having thorough experience with them in assessing spasticity, ataxia, sensation, and muscle strength in individuals with AMN and in individuals with multiple sclerosis. We predict that MT imaging and DTI, which measure the integrity of white matter and fiber tracts in the brain and spinal cord, will aid in understanding the extent to which axonal/myelin anatomy are associated with sensory and motor impairments as well as locomotor patterns with the goal of understanding how to treat physical disability more effectively.

4. Study Procedures

- a. Study design, including the sequence and timing of study procedures (distinguish research procedures from those that are part of routine care).

Date: July 1, 2013
Principal Investigator: [name]
Application Number: NA_00045673

We will test female heterozygote carriers of X-ALD and healthy age- and gender-matched controls.

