Healthy controls have the same exclusion criteria as women with AMN with 2 exceptions, (1) they can be age 21-70 years, and (2) they will not be carriers for X-ALD. They must have normal neurological function.

6. Drugs/ Substances/ Devices

- a. The rationale for choosing the drug and dose or for choosing the device to be used.

N/A

- b. Justification and safety information if FDA approved drugs will be administered for non-FDA approved indications or if doses or routes of administration or participant populations are changed.

N/A

- c. Justification and safety information if non-FDA approved drugs without an IND will be administered.

N/A

Study Statistics

- a. Primary outcome variable.

Primary outcome variables for sensorimotor impairments include: vibration sensation, strength (average values from the hip and ankle muscles, both flexion and extension, will be used), and spasticity from the ankle flexor/extensor muscles bilaterally.

The primary variables of interest for white matter integrity in this analysis will be fractional anisotropy (FA) and magnetization transfer ratio (MTR).

Other primary outcome variables include correlations to determine relationships between sensorimotor impairments and between white matter integrity variables in the tracts of interest. Multiple regression analysis we will also be used determine to what extent sensorimotor impairments are related to white matter integrity variables.

The primary outcome variable for the exercise intervention we will calculate a functional composite score (FS) for each person that will incorporate 4 tests that functionally challenge the lower extremity: 1) sit to stand, 2) Up and Go test, 3) 25-foot timed walk, and 4) 6-minute walk test.

- b. Secondary outcome variables.

To determine response to three months of the exercise intervention:

1. We will calculate pre- to post- trial differences between groups using an unpaired t test. Changes between pre- and post-trial within groups will also be compared with paired t tests.

Date: July 1, 2013
Principal Investigator: [name]
Application Number: NA_00045673

2. To determine change in hip flexion, FS from post- to follow up session within groups will be compared with paired t tests. [(Exercise_{followup}-Exercise_{post}) vs (Exercise_{post}-Exercise_{pre})], will be evaluated.

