 3. To evaluate possible time and group interactions during the intervention within groups we will use multivariate ANOVA's. Significant interactions will be evaluated with a mixed effects linear regression.
 4. To determine change in EDSS scores over each session we will use with Wilcoxon signed rank test.
 5. To determine whether specific changes in the primary outcome measures are predicted by the changes in tract specific demyelination and axonal loss (i.e., MTR and FA) we will determine how much each impairment changed from the pre- to post- session.
 6. We will conduct separate correlations to determine the relationship between the primary outcomes, and extent of demyelination and axonal loss pre- and post-intervention.
 7. Multiple regression analyses will also be used to determine which pattern of white matter damage (i.e., demyelination, axonal loss) best predicts hip flexion and FS.
- c. Statistical plan including sample size justification and interim data analysis.

Preliminary studies of heterozygote data from our laboratory suggest that a minimum of 12 subjects are needed to obtain adequate statistical power. Hip flexion strength data from female carriers are: 11.2 ± 4.6 kg. Using these values, differences between groups on the order of one SD will be statistically significant with a power of 0.8 given a sample size of 12 subjects. To account for attrition, we have added 25% to this total. Therefore, our initial plan is to have 15 female carriers for this project and 15 healthy controls. All power calculations assume two-tailed tests with $\alpha = 0.05$. Analysis will be done using Statistica software (StatSoft Inc., Tulsa OK) or Stata (StataCorp).

- d. Early stopping rules.

None.

7. Risks

- a. Medical risks, listing all procedures, their major and minor risks and expected frequency.

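### Controls are called age-matched, but the plan gives no matching procedure, and no carrier-versus-control analysis uses age

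*Combined protocol and SAP*

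**What the plan says.** Section 4a (study design) describes the comparison group as "healthy age- and gender-matched controls". Section 5 admits carriers aged 21 to 65. For controls it makes an explicit exception: "they can be age 21-70 years". The control recruitment text in Section 4a covers advertisements, telephone screening and scheduling. It gives no matching ratio, age window, pairing step or balance check.

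Section 4c states that everyone, controls included, does the exercise programme. Under Study Statistics, part b, item 1 compares the groups on change: "We will calculate pre- to post- trial differences between groups using an unpaired t test". Item 3 adds "To evaluate possible time and group interactions during the intervention within groups we will use multivariate ANOVA's" and then "Significant interactions will be evaluated with a mixed effects linear regression". Neither item names age or a matched-set term.

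The sample-size text (part c) is written for a level of strength: "Hip flexion strength data from female carriers are: 11.2 ± 4.6 kg". It claims that "differences between groups on the order of one SD will be statistically significant" with power 0.8 and 12 subjects, two-sided alpha 0.05. Adding 25% for attrition gives 15 carriers and 15 controls.

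**The concern.** Carriers and controls are not randomised, so comparability on age depends on the matching. By choosing age as a matching factor, the plan treats it as relevant to outcome. Yet the only operational age rule is a pair of eligibility ranges, and these differ between the groups. Nothing in the analysis corrects an imbalance if one arises.

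Two things are at stake. First, a difference in mean age could enter the group contrast. Second, if matching succeeds, an analysis that ignores the matching factor leaves explained variance in the error term, so the standard error is wider than it need be. With 12 to 15 women per group, both deserve attention.

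**Working it through.** **Inputs from the plan.** SD 4.6 kg; difference one SD; 12 evaluable per group (taken as per group because 12 × 1.25 = 15 and 15 + 15 are enrolled); two-sided alpha 0.05; age ranges 21–65 and 21–70.

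**Assumptions.** The documents do not relate age to outcome. I take age to explain R² = 4% to 20% of outcome variance (correlation 0.2 to 0.45). Where an age SD is needed, I take ages as uniform over 21–65: 44/√12 = 12.7 years.

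**The plan's own figure.** An unpaired t test with d = 1 and 12 per group has power 0.65 (noncentral t), not 0.80; with 15 per group it is 0.75. That shortfall is a separate matter. Here 0.65 is only the starting point.

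**Effect of the 66–70 band alone.** If k of 15 controls are five years older than their matches, mean age shifts by 5k/15 years. For k = 1 to 5 that is 0.3 to 1.7 years. Bias in SD units = correlation × gap / 12.7:
- smallest: 0.2 × 0.33/12.7 = 0.005 SD, or 0.02 kg
- largest: 0.45 × 1.67/12.7 = 0.06 SD, or 0.27 kg

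The standard error of the group difference is √(2/12) = 0.41 SD, or 1.9 kg, so this bias is small.

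**Effect if matching does not operate at all** (uniform ages over each permitted range, 15 per group, by simulation):

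| | Controls 21–70 | Controls 21–65 |
|---|---|---|
| Expected gap in mean age | 45.5 − 43.0 = 2.5 years | 0 |
| Chance of a gap over 5 years | 0.37 | 0.28 |
| Chance of a gap over 10 years | 0.07 | 0.03 |

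A 2.5-year gap gives 0.04 to 0.09 SD on a level score, and a 10-year gap gives 0.16 to 0.35 SD. Equalising the ranges removes only part of the risk. The larger gap is the absence of both a matching rule and age adjustment.

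**Efficiency on a level score.** Adjusting for age divides the error SD by 1/√(1 − R²), so the effective d is 1/√(1 − R²). Power at 12 per group, with one degree of freedom charged (21 instead of 22):
- R² = 0.04: d = 1.02, power 0.66
- R² = 0.20: d = 1.12, power 0.74

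Without that charge the figures are 0.67 and 0.74.

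**Validity of the unpaired test.** If matching is on age alone, the within-pair correlation is roughly R². In simulation at 12 per group, the type I error of the unpaired test is about 0.04 at a correlation of 0.1 and 0.03 at 0.2. Both are below the nominal 0.05.

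**Change scores.** The planned t test is on pre-to-post differences, so a stable effect of age on level cancels within each woman. Age enters only so far as it alters the 12-week response to training. The power gain above does not carry over to that test.

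**The case against.** The strongest reply is that an eligibility range is not a matching rule. A control limit five years above the carrier limit fits a matching window of about five years. Under such a window, capping controls at 65 would leave carriers near 65 with only same-age or younger matches. This stands. A reader might infer from the two ranges that imbalance is built in, or that the limit must be lowered; the documents support neither.

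A reader might also infer that the unpaired t test is invalid after matching. It is not. It is valid and errs on the conservative side.

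A third tempting reading is that older controls will mask impairment in the carriers. That concerns levels, whereas the listed t test concerns change. The plan lists no baseline carrier-versus-control test of FA, MTR, strength or the functional score, and both primary objectives concern associations and prediction within carriers. This limits the concern. It does not remove it, because the power statement is framed as a group difference on the strength scale, so a level contrast is at least envisaged.

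What the reply leaves untouched is that no matching procedure is written and no listed group analysis uses age.

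**Conclusion.** The concern holds in a limited form. The plan relies on age matching that it does not define, and compares non-randomised groups without age in the model. Residual imbalance is not removed and the matching factor is not used.

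The size is modest. The 66–70 band alone is worth at most about 0.06 SD on a level score under the assumptions above. A larger shift, up to about 0.35 SD for a 10-year gap, needs matching to fail and chance to be unkind. Adjustment would take power for a one-SD level contrast at 12 per group from 0.65 to about 0.66–0.74, and may add almost nothing for change scores. The R² range and the uniform ages are assumptions. This is an inexpensive improvement, not the correction of an invalid test.

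**What to change.** - Replace the unpaired t test of pre-to-post change with a linear model of change on group and age.
- Include age in the time-by-group mixed model. Enter age and age-by-time, because an age main effect alone adjusts levels and leaves the group-by-time contrast unadjusted.
- Adjust for age in any carrier-versus-control comparison of levels, such as the hip flexion contrast behind the power statement.
- State how controls are matched (individual or frequency, ratio, age window), and whether the limit of 70 follows from that window. The limit itself need not change.

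An age covariate works under individual or frequency matching and does not lose a pair when one member drops out.

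Cost: analysis-plan wording and one degree of freedom in the change model (slightly more in the mixed model with age-by-time). If the groups end far apart in age, the adjusted standard error also widens. With a 10-year gap and the age SD above, the squared age–group correlation is 25/(12.7² + 25) = 0.13, a factor of 1/√0.87 = 1.07 before any gain from R². That is the price of removing the bias.
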